I agree to conduct this clinical investigation in accordance with the design and specific provisions of this protocol and all applicable regulatory requirements. Modifications to the clinical investigation are acceptable only with a mutually agreed upon protocol amendment as approved by the sponsor, regulatory bodies and Institutional Review Board/ Ethics Committee. I agree to await Institutional Review Board/ Ethics Committee approval of the protocol, informed consent, and sponsor approval before initiating the study, and to obtain consent from subjects prior to their enrollment in the study. I agree to collect and record data as required by the protocol and case report forms, and to maintain study documents for the period of time required.

Confidential

This document contains confidential information belonging to Senseonics, Inc. Except as may be otherwise agreed to in writing, by accepting or reviewing these materials, I agree to hold such information in confidence and not to disclose it to others (except where required by applicable law), nor use it for unauthorized purposes.

Investigator's signature

Date of signature

SYNOPSIS

Title of Protocol	PRECISION Study: A Prospective , Multicenter Evaluation of Precision , Compression , Accuracy and Updated Algorithm of a Novel Continuous Implanted Glucose Sensor
Sponsor	Senseonics, Inc.
Investigational Device	Senseonics Continuous Glucose Monitoring (CGM) System (the "System")
Reference Instrument	Reference Glucose Analyzer (bedside, YSI 2300 STAT PLUS® Glucose and Lactate Analyzer, Yellow Springs Instruments, Yellow Springs, OH, USA).
Calibration Standard	FDA-cleared Blood Glucose Meter (Subject SMBG Meter)
Study Purpose	The purpose of this clinical investigation is to evaluate the precision and accuracy of the Senseonics Continuous Glucose Monitoring System (Senseonics CGM System) measurements when compared with reference standard measurements. Compression of the sensor site and use of a new algorithm will also be evaluated. The investigation will also evaluate safety of the Senseonics CGM System usage.
Target Indication for Use	The Senseonics CGM System is a glucose monitoring device intended to continually measure interstitial fluid glucose levels in individuals with diabetes for the operating life of the sensor. The Senseonics CGM System is intended to be used: 
 • To provide real-time glucose readings directly to the user. • To provide glucose trend information. • To provide alerts for the detection and prediction of episodes of low blood glucose (hypoglycemia) and high blood glucose (hyperglycemia).
Study Design Summary	This is a non-randomized, prospective, single-arm, multi-center study, enrolling adult subjects with diabetes mellitus in the United States at up to 4 sites. The investigation will include both clinic visits and home use of the Senseonics CGM System. Subjects will have one or two Sensors inserted in the upper arms by trained Investigators. The accuracy of the system will be evaluated during clinic visits, comparing Sensor glucose with laboratory reference values. For qualifying subjects, during the clinic visits, there are planned hyperglycemia and hypoglycemia challenges, as described in protocol Section 5. All diabetes care decisions will be based on plasma glucose values, rather than System CGM results.

	
Visit Schedule:
 
 • Visit 1 Screening Visit. Following informed consent process, screening evaluation will determine subject eligibility for enrollment. Visit lasting approximately 2 hours. Visit includes screening medical and diabetes history, examination and laboratory assessments. • Visit 2 Sensor Insertion Visit (Day 0, visit window: Visit 1 +0-30 Days). Sensors will be inserted by Investigator in the upper arms. A minimum of 6 and a maximum of 9 subjects will receive one sensor. Remaining subjects will receive two sensors, one in each arm. Subject receives training on study and devices. In addition for a group of subjects, 3 blood draws post-insertion will be done to measure dexamethasone levels. Visit lasting approximately 2-6 hours. • Sensor Accuracy Visits. The following visits include Sensor accuracy assessment with reference laboratory glucose comparison, Sensor calibration with BG meter, and safety assessments including blood draws to measure dexamethasone levels. Protocol Section 4 describes the procedure details, including hyperglycemia challenges and hypoglycemia challenge for eligible subjects. 
 • Visit 3 (Day 1 \pm 1 Day). Visit lasting approximately 19 hours. • Visit 4 (Day 7 \pm 1 Day). Visit lasting approximately 18 hours. • Visit 5 (Day 14 \pm 1 Day). Visit lasting approximately 18 hours. • Visit 6 (Day 30 \pm 7 Days). Visit lasting approximately 14 hours. • Visit 7 (Day 60 \pm 7 Days). Visit lasting approximately 14 hours. • Visit 8 (Day 90 -3/+7 Days). Visit lasting approximately 15 hours. 
Following evaluation of Sensor accuracy, Sensors are removed at end of visit.
 • Visit 9 Follow-up Visit. Sensor Site Assessment is performed approximately 10 days after Sensor removals (- 3/ +7 day window) to assess Sensor sites. At this visit, if there is a concern by investigator about healing of sensor site, subject will return in approximately 10 days and followed until resolution. 
Home Use: Subjects will follow their usual diabetes care routine as per their medical team recommendations while wearing the System. All diabetes management decisions by the subject and health care team will be made based on standard of care with blood glucose monitoring, and not based on Senseonics CGM glucose values. Subjects will be advised to wear the Transmitter over the Sensor for data collection, except during transmitter charging, bathing or water activity.

--	---

Subjects will calibrate the CGM using the study-provided Subject SMBG Meter a minimum of two times per day according to Instructions for Use (Four times per day during Initialization Phase). Subject will use the same study-provided BG meter for monitoring their diabetes care, and this meter will be downloaded during the clinic visits. Subjects will be requested to check the BG meter glucose for all diabetes care decisions at a minimum 4-7 times per day.

Clinic Visits: Blood samples, meter BG, and Sensor glucose values will be collected. Diabetes care decisions during the visit will be made based on blood glucose determinations, rather than Senseonics CGM System results.

During sampling period blood sample glucose measurements will be performed and collected for laboratory glucose reference analysis approximately every 15 minutes, and more frequently (approximately every 5 minutes) during periods of hypoglycemia and hyperglycemia as described in the protocol.

Safety Assessments and Management

As described in Section 7.1, there will be trained staff and an emergency cart available at the site at all times. Safety guidelines will be utilized for subject care during periods of hyperglycemia (including monitoring blood ketones) and hypoglycemia. A physician or nurse practitioner will be available at all times during hypoglycemia and hyperglycemia challenges.

The sensor insertion sites will be assessed at each clinic visit. A review and documentation of adverse events occurring in the clinic and during home use will be on-going.

Laboratory tests will be monitored as per protocol for safety assessment. Additional details of the study design and safety assessments and management are described in the protocol. Blood draws for Dexamethasone measurement will be made at Screening and on Visits 2-8. A subset of a minimum of 6 and a maximum of 9 subjects will also have blood draws for dexamethasone measurement at days 3-6 of sensor use to identify possible blood draw time points during the first week of sensor wear for the remaining subjects.

Estimated Study Duration of Study and Subject Participation	Enrollment Period: Approximately 2 months Individual Subject Participation: Approximately 4.5 months Duration of Study: Approximately 6 months
Study Sites	Up to 4 investigative sites located in the United States.
Subject Population	The subject population consists of adult subjects with diabetes mellitus. Based on sample size calculations, approximately 44 adult subjects will be enrolled and approximately 36 will be inserted with the CGM Sensor in the investigation.
Inclusion Criteria	Male and Female Subjects meeting all of the following inclusion criteria will be included in this study: 
 1. Adult subjects, age ≥ 18 years 2. Clinically confirmed diagnosis of diabetes mellitus for ≥ 1 year 3. Subject has signed an informed consent form and is willing to comply with protocol requirements
Exclusion Criteria	Subjects meeting any of the following exclusion criteria at the time of screening will be excluded from this study: 
 1. History of severe hypoglycemia in the previous 6 months. Severe hypoglycemia is defined as hypoglycemia resulting in loss of consciousness or seizure 2. History of diabetic ketoacidosis requiring emergency room visit or hospitalization in the previous 6 months 3. Female subjects of childbearing capacity (defined as not surgically sterile or not menopausal for ≥ 1 year) who are lactating or pregnant, intending to become pregnant, or not practicing birth control during the course of the study. 4. A condition preventing or complicating the placement, operation, or removal of the Sensor or wearing of transmitter, including upper extremity deformities or skin condition. 5. Symptomatic coronary artery disease; unstable angina; myocardial infarction, transient ischemic attack or stroke in the past 6 months; uncontrolled hypertension (systolic >160 mm Hg or diastolic >100 mm Hg at time of screening); current congestive heart failure; history of cardiac arrhythmia (benign PACs and PVCs allowed). Subjects with asymptomatic coronary artery disease (e.g, CABG, stent placement or angioplasty) may participate if negative stress test within 1 year prior to screening and written clearance from Cardiologist documented. 6. Hematocrit $<30\%$ or $>55\%$ 7. History of hepatitis B, hepatitis C, or HIV 8. Current treatment for a seizure disorder unless written clearance by neurologist to participate in study 9. History of adrenal insufficiency

	
10. Currently receiving (or likely to need during the study period): immunosuppressant therapy; chemotherapy; anticoagulant/antithrombotic therapy (excluding aspirin); glucocorticoids (excluding ophthalmic or nasal). This exclusion does include the use of inhaled glucocorticoids and the use of topical glucocorticoids (over sensor site only); antibiotic for chronic infection (e.g. osteomyelitis, endocarditis)
 
11. A condition requiring or likely to require magnetic resonance imaging (MRI)
 
12. Known topical or local anesthetic allergy
 
13. Known allergy to glucocorticoids
 
14. Any condition that in the investigator's opinion would make the subject unable to complete the study or would make it not in the subject's best interest to participate in the study. Conditions include but are not limited to psychiatric conditions, known current or recent alcohol abuse or drug abuse by subject history, a condition that may increase the risk of induced hypoglycemia or risk related to repeated blood testing. Investigator will supply rationale for exclusion
 
15. Participation in another clinical investigation (drug or device) within 2 weeks prior to screening or intent to participate during the study period
 
16. The presence of any other active implanted device (as defined further in protocol)
 
17. The presence of any other CGM sensor or transmitter located in upper arm (other location is acceptable)

Investigation Objectives	
Effectiveness Objective: To determine accuracy of the Senseonics CGM System measurements through approximately 90 days post-insertion. An interim analysis will be conducted on all subjects after completion of Visit 6 (day 30 accuracy visit).
 
Safety Objective: To demonstrate safety of the Senseonics CGM System through 90 days post-insertion or sensor removal and follow-up by measuring the incidence of device-related and insertion/removal procedure-related serious adverse events during the investigation.

Endpoints	
Effectiveness Endpoint: The effectiveness endpoint will be mean absolute relative difference (MARD) for paired Sensor and reference measurements through 90 days post-insertion for reference glucose values from 40-400 mg/dL. This endpoint will be evaluated descriptively. Neither inferential analysis nor hypothesis testing will be performed. An interim analysis will be conducted on all subjects after completion of Visit 6 (day 30 accuracy visit).

	
Safety Endpoint: Incidence of device-related or sensor insertion/removal procedure-related serious adverse events through 90 days post-insertion or sensor removal and follow-up.

Other Safety Endpoints	
 1. Incidence of all device-related or sensor insertion/removal procedure-related adverse events in the clinic and during home use. 2. Incidence of all adverse events in the clinic and during home use. 3. Incidence of hospitalizations due to hypoglycemia, hyperglycemia or ketoacidosis occurring during home use. 4. Incidence of reported hypoglycemic and hyperglycemic events occurring during home use.

ABBREVIATIONS

AE	Adverse Event
BG	Blood Glucose
BG Meter	Blood Glucose Meter (also known as SMBG Meter)
β-HOB	β-hydroxybutyrate or “ketones,” also abbreviated B-HOB
BMI	Body Mass Index
CD	Compact disc
CFR	Code of Federal Regulations
CGM	Continuous Glucose Monitoring
CRF	Case Report Form
CRO	Contract Research Organization
DCF	Data Clarification Form
DKA	Diabetic Ketoacidosis
eCRF	Electronic Case Report Form
EKG	Electrocardiogram (also commonly abbreviated as ECG)
FDA	Food and Drug Administration
GCP	Good Clinical Practice
HbA1c	Hemoglobin A1c or A1C
HCT	Hematocrit
HIV	Human Immunodeficiency Virus
HHD	Hand Held Device
ICH	International Conference on Harmonization
IRB	Institutional Review Board
ISO	International Organization for Standardization
MARD	Mean absolute relative difference
MAD	Mean absolute difference
MDI	Multiple Daily Injections
MMA	Mobile Medical Application
MRD	Mean relative difference
PARD	Percent absolute relative difference
PI	Principal Investigator
POC	Point of Care
SAE	Serious Adverse Event
SMBG	Self-Monitoring Blood Glucose
SQ	Subcutaneous
UADE	Unanticipated Adverse Device Effect
USB	Universal Serial Bus
YSI	Yellow Springs International (Blood glucose analyzer)

1	INTRODUCTION, IDENTIFICATION OF THE INVESTIGATIONAL DEVICE, AND RATIONALE	15
1.1	Names, Intended Use, and Description of Study Device	15
1.2	Summary of Pre-clinical and Clinical Experience	18
2	STUDY OBJECTIVES	19
2.1	Effectiveness	19
2.2	Safety	19
3	STUDY DESCRIPTION	19
3.1	Study Population	19
3.2	Inclusion and Exclusion Criteria	19
3.3	Study Design	21
4	STUDY METHODS, PROCEDURES AND CLINIC VISITS	23
4.1	Visit 1 – Screening/Enrollment	25
4.2	Visit 2 – Sensor Insertion/Training	26
4.3	Subset of subjects for dexamethasone analysis	29
4.4	Sensor Accuracy (Sampling) Visit 3 – Day 1 (\pm 0 Days)	29

1 INTRODUCTION, IDENTIFICATION OF THE INVESTIGATIONAL DEVICE, AND RATIONALE

In spite of recent improvement in therapies, diabetes mellitus continues to be a difficult medical condition to treat. The challenge remains to achieve desired glycemic control and to prevent both the short-term consequences (severe hypoglycemia and DKA) and long-term complications (retinopathy, neuropathy, nephropathy and cardiovascular problems). The monitoring of blood glucose by the patient with diabetes is one of the key tools of diabetes self-care. The current standard glucose monitoring regimen for patients with diabetes involves using a small portable meter to obtain a capillary fingertip glucose measurement multiple times a day. According to the International Society of Pediatric and Adolescent Diabetes (ISPAD), “successful application of intensified diabetes management with multiple injection therapy or insulin infusion therapy requires frequent self-monitoring of blood glucose (four to six times a day) and regular, frequent review of the results to identify patterns requiring adjustment to the diabetes treatment plan.”¹ Despite this diagnostic procedure and therapeutic interventions, due to the nature of diabetes glucose values may fluctuate widely throughout the day. In addition, as the BG meter value shows only a point in time glucose level, even patients who monitor frequently, may miss significant hypoglycemic and hyperglycemic excursions. Continuous glucose monitoring (CGM), which measures interstitial glucose levels, has been developed recently and has been shown to be associated with improved glycemic control in adults with type 1 diabetes. Current commercially available CGM devices require the repeated, frequent insertion of a sensor by the patient.

Senseonics, Inc. a medical device manufacturer headquartered in Germantown, Maryland, USA, is developing a new CGM System intended for measuring interstitial fluid glucose levels in adults with diabetes mellitus. The Senseonics CGM System measures interstitial fluid glucose levels continuously and is implanted under the skin by a trained clinician. Unlike commercially available transcutaneous continuous glucose monitoring devices with short operating lives (up to 7 days), the Senseonics Sensor is intended to be inserted subcutaneously with no sensor part protruding from the skin, and the operating life is intended to be up to 90 days or until the end of life indicator is reached.

This clinical trial is being carried out to assess the safety and efficacy of the Senseonics CGM System. It is intended that the results of this study will support the targeted indication as described in Section 1.1 below, providing quantification of accuracy and demonstrate safety in clinic and home use settings over the operating life of the Sensor.

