1.1 Names, Intended Use, and Description of Study Device

The study investigational Device is the Senseonics CGM System (“System”).

The Senseonics Continuous Glucose Monitoring System is a glucose monitoring device intended to continually measure interstitial fluid glucose levels in individuals with diabetes for the operating life of the sensor. The Senseonics Continuous Glucose Monitoring System is intended to be used:

- To provide real-time glucose readings directly to the user
- To provide glucose trend information
- To provide alerts for the detection and prediction of episodes of low blood glucose (hypoglycemia) and high blood glucose (hyperglycemia).

The Senseonics CGM System consists of:

1. Glucose Sensor, (approximately 3.5 mm [0.138"] diameter x 18.3 mm [0.720"] length) which has a ring that elutes the steroid dexamethasone
2. Battery-powered external Transmitter ("Transmitter", Gen1/Gen2)
3. Mobile Medical Application (MMA) for display of glucose information that runs on a Handheld Device (HHD).

Accessories to the system include:

1. Blunt dissector for creating a pocket under the skin
2. Insertion tool used to place the Sensor into the pocket.
3. Transmitter accessories (power supply, adhesive patches)

Senseonics' continuous glucose monitoring system has been branded for commercial use as the Eversense Continuous Glucose Monitoring (CGM) System. System components may be branded as Senseonics or as Eversense. The use of the system in this clinical study is outside the current commercial indications for use.

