11.1.6 Analysis Populations

Effectiveness Analysis population: The effectiveness analysis and exploratory effectiveness endpoints will be based on all data from all subjects in this investigation with at least one paired glucose reading (one Sensor with one reference glucose). The Senseonics CGM System and reference readings are compared by pairing each reference reading with the first Sensor reading that occurred up to 5 minutes after sample acquisition.

Safety Analysis Population: Safety analysis will be based on all subjects that undergo the sensor insertion in this investigation.

Dexamethasone Analysis Population: The approximately 6 subjects with Sensor's inserted will constitute the dexamethasone analysis population to determine if and when a peak dexamethasone level occurs. Subsequent to determining if and when a peak occurs, all subjects with Sensor's inserted will constitute the complete dexamethasone analysis population.

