6.10.1.16 Evaluation of glucose alert performance

The glucose alert performance of the Senseonics CGM System will be evaluated retrospectively on Senseonics CGM and reference measurements collected to determine accuracy of hypo- and hyperglycemic states and associated sensitivity and specificity (Tables 14A and 14B in APPENDIX 1). All rates are calculated assuming both threshold and 10-min ahead predictive alerts are turned on. Only performance against YSI is evaluated. For the alert performance evaluation, the following definitions will be used.

Hypoglycemia Alert Rate:

The Alert Rate shows how often the alert was right or wrong. The True Alert Rate is the % of time the device alerted when the blood glucose level was at or below the hypoglycemia alert setting

within 15 minutes before or after the device alerted. The False Alert Rate is the % of time the device alerted when the blood glucose level was above the hypoglycemia alert setting within 15 minutes before or after the device alerted.

Hypoglycemia Detection Rate:

The Detection Rate shows how often the device recognized and alerted that there was an episode of hypoglycemia or how often it missed such an event. The Confirmed Event Detection Rate is the % of time the blood glucose level was at or below the hypoglycemia alert setting and device alerted within 15 minutes before or after the blood glucose was at or below the alert settings. The Missed Event Detection Rate is the % of time the blood glucose was at or below the hypoglycemia alert setting, but the device did not alert within 15 minutes before or after the blood glucose was at or below the alert setting.

Hyperglycemia Alert Rate:

The Alert Rate shows how often the alert was right or wrong. The True Alert Rate is the % of time the device alerted when the blood glucose level was at or above the hyperglycemia alert setting within 15 minutes before or after the device alerted. The False Alert Rate is the % of time the device alerted when the blood glucose level was below the hyperglycemia alert setting within 15 minutes before or after the device alerted.

Hyperglycemia Detection Rate:

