6.10.1.25 Effect of rate of change on sensor performance

Sensor Agreement for the different categories of rates of change as displayed by the system will be compared to determine whether there is any evidence of differences (Table 21 in APPENDIX 1).

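### The stated indication includes trend information and predictive alerts, but the exploratory analyses cannot show whether either function works

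*Protocol*

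**What the plan says.** **Indication.** Protocol Section 1 states: "It is intended that the results of this study will support the targeted indication as described in Section 1.1 below". The sentence then names quantified accuracy and demonstrated safety as what the study supplies. Section 1.1 lists three functions, and SAP Section 2 repeats them. The first is live readings shown to the user. The second concerns trend: "To provide glucose trend information". The third concerns alerts, and it covers more than detection: "To provide alerts for the detection and prediction of episodes of low blood glucose (hypoglycemia) and high blood glucose (hyperglycemia".

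**Alerts.** The only alert analysis is SAP 6.10.1.16, which is retrospective and made against YSI. It states: "All rates are calculated assuming both threshold and 10-min ahead predictive alerts are turned on". A low is confirmed if the "device alerted within 15 minutes before or after the blood glucose was at or below the alert settings". The rule for highs mirrors this, and the True Alert Rate uses the same two-sided window around the alert. Tables 14A and 14B give four rates at each of four low settings (60 to 90 mg/dL) and seven high settings (120 to 300 mg/dL). They have no column by alert type and no lead time.

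**Trend.** SAP 6.10.1.25 states: "Sensor Agreement for the different categories of rates of change as displayed by the system will be compared". The rows of Table 21 are five categories of system rate. The cells are the percentages of readings within 20/20%, 30/30% and 40/40% of reference.

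**Pairing.** Protocol 11.1.6 and SAP 6.4 compare readings by "pairing each reference reading with the first Sensor reading that occurred up to 5 minutes after sample acquisition". Protocol 10.2.1 puts sensor readings usually 5 minutes apart.

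**Sampling.** Protocol 5.9.2 draws blood every 5 minutes at or below 75 and at or above 325 mg/dL, and every 15 minutes in between.

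**The concern.** A predictive alert is useful because it comes before the event. A rate that pools it with threshold alerts and gives equal credit to late alerts measures whether some alert came near a low or high. It does not measure whether prediction worked. Likewise, trend information is right or wrong only relative to how blood glucose was actually moving, and the only rate analysis contains no independent rate. The study report could therefore show good alert and rate-of-change tables for a device whose predictive alerts never fire, or whose displayed trend is often wrong.

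The pairing rule raises a smaller, related question for real-time readings. The scored value is the next reading after the draw, not the one already available at the time of the draw.

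**Working it through.** The plan has no figure of its own to reproduce here. The checks apply its definitions.

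**1. Alert window.** Let c be the time glucose truly crosses a low setting, a the alert, and y the first YSI value at or below the setting. The SAP credits the event if |a − y| ≤ 15 minutes. Alerts at −10, 0, +5, +10 and +15 minutes relative to y all count; one at +16 does not.

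Now take a threshold-only device that triggers 0, 5 or 10 minutes after c and alerts at its next 5-minute reading. Then a lies between c and c + 15. With nominal draws no more than 15 minutes apart, y also lies between c and c + 15. So |a − y| never exceeds 15, and confirmed detection is 100%. A noise-free simulation (20,000 falls per combination, assumed 1 and 2 mg/dL/min) also gave 100% at 60, 70, 80 and 90 mg/dL. No alert preceded the true crossing, so true prediction was 0%. In this example the True Alert Rate is also 100%, because every alert has a YSI value at or below the setting within 15 minutes.

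**2. What the time stamps can recover.** Low settings 60 and 70 lie in the 5-minute range. Low 80 and 90 and all seven high settings, 9 of 11, lie in the 15-minute range. The same simulation gives the share of truly late alerts that still appear to precede the first YSI value at or below the setting:

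| Low setting (mg/dL) | Fall (mg/dL/min) | Triggered at crossing | 5 min late | 10 min late |
|---|---|---|---|---|
| 60 | 1 | 50.5% | 0.0% | 0.0% |
| 60 | 2 | 61.9% | 4.3% | 0.0% |
| 70 | 1 | 66.9% | 16.8% | 0.0% |
| 70 | 2 | 79.4% | 33.2% | 4.2% |
| 80 | 1 | 83.3% | 49.7% | 16.5% |
| 80 | 2 | 83.2% | 49.6% | 16.7% |
| 90 | 1 | 83.7% | 50.0% | 16.5% |
| 90 | 2 | 83.3% | 50.1% | 16.9% |

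The row for 70 is worse than that for 60 because the draw before the crossing may still be above 75, which leaves a 15-minute gap.

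A strict forward window errs the other way. For a perfect alert 10 minutes before the crossing, with 15-minute draws at a uniform phase, y − a = 10 + U, where U is uniform on 0 to 15. A 15-minute limit passes it with probability (15 − 10)/15 = 1/3.

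**3. Trend.** Each entry in Table 21 depends on three quantities: system glucose, YSI glucose and system rate. Hold these fixed and change the YSI rate, and the table does not change. It therefore carries no information on whether the displayed rate was right. The SAP reference list includes works on continuous error-grid analysis and sensing time lag, but no planned analysis uses them.

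**4. Pairing.** Let u be the wait from the draw to the next reading, uniform on 0 to 5 minutes with mean 2.5. The previous reading is at u − 5, mean −2.5, so the two are 5 minutes apart. At an assumed 1 to 2 mg/dL/min, glucose moves 5 × 1 = 5 to 5 × 2 = 10 mg/dL in that time.

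On a steady ramp of rate r with sensor lag L, the scored error is r|u − L| and the previous-reading error is r|u − 5 − L|.

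- L = 0: both average 2.5r, so the difference is 0.
- L = 5 to 10 minutes (assumed): the difference is 5r. At 150 mg/dL this is 5/150 = 3.3 points for r = 1 and 10/150 = 6.7 points for r = 2.
- r = 0: the difference is 0.

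The documents give neither the lag nor the rates of change.

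**The case against.** **The objectives are accuracy and safety.** The introduction's sentence goes on to name these. Protocol Section 2 and SAP 4.1 set only these objectives, and SAP 4.4 ties the sample size to an FDA request for accuracy data through day 30 and dexamethasone levels. The alert and rate analyses are exploratory, descriptive and without a pass mark. Supporting an indication does not mean being its only evidence, and Protocol 1.2 records two earlier pivotal studies. All of this stands. A reader might infer that the trial cannot answer its own question whatever the data show. The documents do not support that: no objective is to validate prediction or trend, and the time-stamped data allow a partial answer.

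**The 100% example is an extreme, and the SAP never speaks of a crossing.** Both are true. The SAP window surrounds any time at which glucose is at or beyond the setting, and the example takes the first such YSI value. That wording makes the credit no narrower, and the example only shows that the rate cannot tell the two devices apart.

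**Draws every 15 minutes cannot resolve a 10-minute horizon.** This stands for 9 of 11 settings and limits the fix.

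**The pairing effect is assumed.** This also stands. A reader might infer that the planned MARD is too favorable by a known amount, or that every pair scores a value the user had not yet seen. Neither follows. Direction and size depend on a lag that the documents do not give. Gen 2 transmitters show no glucose and calculate none during wear (Protocol 1.1.2, 4.2.5). They serve up to 30 of 66 sensors (6 one-sensor plus 30 two-sensor subjects), and for them no reading was on display under any pairing rule.

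**Conclusion.** The point holds as a gap between the indication and the exploratory analyses. As written, no planned output can show whether prediction or trend works: a late threshold alert scores the same as a prediction, and the displayed rate is never compared with an independent one. It is not a failure of the accuracy or safety objectives.

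The alert result follows from the window definition and nominal draw times. The simulated shares also assume noise-free falls of 1 to 2 mg/dL/min. The pairing part supports only a sensitivity analysis: the two readings are about one 5-minute cycle apart, but the effect on overall MARD is unknown, and it is zero if glucose is stable or the sensor has no lag.

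**What to change.** 1. **SAP 6.10.1.16, Tables 14A and 14B.** Keep the planned windows and report the rates for threshold alerts alone, predictive alerts alone, and both. Split confirmed detections into alert before and alert after the YSI crossing. Report this split and the lead time mainly at low settings 60 and 70, for events with 5-minute draws on both sides of the crossing. Label results at low 80 and 90 and at all high settings as limited by 15-minute draws. Do not apply a strict 15-minute forward rule there.
2. **SAP 6.10.1.25.** Beside Table 21, add a concurrence table of the five system-rate categories against the same categories of YSI rate from consecutive draws, stating the draw interval.
3. **SAP 6.9.** As a sensitivity analysis for Gen 1 only, report MARD using the last reading at or before the draw (within 5 minutes) beside the planned MARD.

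The cost is SAP text and programming on data already collected, with no extra visits or draws and no change to the endpoint. The drawbacks are coarse estimates where draws are 15 minutes apart, few events meeting the 5-minute condition, and possibly a slightly higher sensitivity MARD. Even with 5-minute draws, an alert triggered at the crossing looks early about half the time (50.5% at 60 mg/dL and 1 mg/dL/min), so a lead time shorter than one draw interval should not be read as prediction.
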